1.2. Study Diagram and Flow

Figure 1-1 Study diagram

Abbreviations: D: day; EFS follow-up: Event-Free Survival follow-up; OS follow-up: Overall Survival follow-up

Figure 1-2 Study Flow

SCREENING

From Day -28 to Day 1 of Cycle 1 (up to 28 days)

Previously untreated patients with histologically confirmed LA-SCCHN (stage III, IVA or IVB as per AJCC/TNM) of the oropharynx, hypopharynx, or larynx, and suitable for definitive chemoradiotherapy

OPC tumors must be known to be HPV-negative (determined by p16 expression using IHC)

RANDOMIZATION 1:1 Xevinapant : Placebo From Day -7 to Day 1 of Cycle 1

Stratification by region (North America vs. Western EU vs. Rest of the World), primary tumor site (larynx vs. other), lymph node involvement (N0-1 vs. N2 vs. N3) and stage (T4 vs. other)

ARM A: Xevinapant + chemotherapy + IMRT

Combination Therapy: Cycles 1-3

Xevinapant, 200 mg/day, Days 1-14 Q3W cycles + concomitant IMRT, from Day 1 for 7 weeks (70 Gy in 35 fractions over 7 weeks, 2.0 Gy/fraction, 5 days/7)

+ cisplatin high dose (100 mg/m²), Day 2 Q3W cycles (or carboplatin at equivalent dose at C2 and/or C3 if the patient cannot receive cisplatin)

Monotherapy: Cycles 4-6 Xevinapant, 200 mg/day, Days 1-14 Q3W cycles

ARM B: Placebo + chemotherapy + IMRT

Combination Therapy: Cycles 1-3

Placebo, Days 1-14 Q3W cycles + concomitant IMRT, from Day 1 for 7 weeks (70 Gy in 35 fractions over 7 weeks, 2.0 Gy/fraction, 5 days/7)

+ cisplatin high dose (100 mg/m²), Day 2 Q3W cycles (or carboplatin at equivalent dose at C2 and/or C3 if the patient cannot receive cisplatin)

Monotherapy: Cycles 4-6
Placebo, Days 1-14 Q3W cycles

EOT

15 days (±7 days) after last study treatment administration (i.e, Xevinapant/placebo, chemotherapy or IMRT whichever is administered last):

clinical and radiological evaluation; HRQL

EFS FOLLOW-UP (data collection of EFS starts from randomization date)

•Day 1 of Month 7 (±2 weeks): clinical and radiological evaluation; HRQL

•Day 1 of Month 9 (±2 weeks): clinical and radiological evaluation

•From Day 2 of Month 9 to Day 1 of Month 30 : clinical and radiological evaluation every 3 months (±2 weeks); HRQL, CCI and ECOG PS evaluation yearly (±2 weeks)

•Day 1 of Month 33 (±2 weeks): clinical and radiological evaluation

•Day 1 of Month 36 (±2 weeks): clinical and radiological evaluation; HRQL, and ECOG PS

•From Day 2 of Month 36 to Day 1 of Month 60 : radiological evaluation every 6 months (±2 weeks); clinical evaluation yearly (±2 weeks); HRQL. Compand ECOG PS evaluation yearly (±2 weeks)

OS FOLLOW-UP

•From Day 2 of Month 60 to EOS: survival status per institutional standard practice at least every 3 months until death or EOS or

•At any time during the study, in case of progression, treatment failure, local or distant relapse or second cancers, subjects will enter the OS follow-up period; they will be followed for survival at least every 3 months until death or EOS

Abbreviations: AJCC: American Joint Committee on Cancer; Cx: Cycle x; EFS: event-free survival follow-up; EOS: end of study; EOT: end of treatment; EU: Europe;; HPV: human papillomavirus; HRQL: health-related quality of life (evaluated with EORTC QLQ-C30, QLQ-HN35 purpose questionnaires); HRQL: health-related quality of life (evaluated with EORTC QLQ-C30, QLQ-HN35 purpose questionnaires); HRQL: health-related quality of life (evaluated with EORTC QLQ-C30, QLQ-HN35 purpose questionnaires); HRQL: health-related quality of life (evaluated with EORTC QLQ-C30, QLQ-HN35 purpose questionnaires); WRT: intensity-modulated radiotherapy; LA-SCCHN: locally advanced squamous cell carcinoma of the head and neck; OPC: oropharyngeal cancer; OS: overall survival; Q3W: every 3 weeks.

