The EFS follow-up period must be performed according to the planned visit schedule within the permitted visit windows. Participants without any progression, treatment failure, local or distant relapse, second cancers or death until Month 60 post-randomization, will enter the overall survival (OS) follow-up period after the Month 60 visit (FUP60). They will be followed for survival status only, at least every 3 months, until the End of Study (EOS) (see Section 7.2). Participants who progress according to RECIST v1.1, will enter the OS follow-up period at time of the event and will be followed up for survival status at least every 3 months, until the EOS (see Section 7.2).

In case of premature discontinuation of treatment in participants without disease progression (e.g., unacceptable toxicity), efficacy assessments will continue to be performed until an EFS event has been determined or Month 60 post-randomization, whichever occurs first.

During the EFS follow-up period and OS follow-up period, each study visit day and allowed time windows will be based on the randomization date.

After completion of the follow-up period, participants who have not discontinued the study prematurely will undergo the EOS assessments ([date of the 60 Month visit of the last on-study participant] ± 2 months) and will be considered as having completed the study (see Section 7.2 in case of premature withdrawal).

If the last on-study participant completes the OS follow-up (60 months after randomization), his/her EOS visit will be performed at the same time as his/her 60 Month visit. In case of premature discontinuation from the study, his/her EOS visit will be performed when he/she discontinues from the study.

The EOS visit can be performed by telephone call.

Table 1-1 Schedule of events / flow chart: screening & treatment period

Study Period		Scr		Combination therapy (CRT and Xevinapant/matched placebo) period															Monotherapy (xevinapant or matched placebo) period			
Cycles		-			1					2					3			4	5	6		
Visit Label		Scr	C1D1	C1D2	C1D4	C1D8	C1D15	C2D1	C2D2	C2D4	C2D8	C2D15	C3D1	C3D2	C3D4	C3D8	C3D15	C4D1	C5D1	C6D1	EOT	
Study Week	Section	(≤4 weeks)	1	1	1	2	3	4	4	4	5	6	7	7	7	8	9	10	13	16	20	
Study Visit Day (from 1st dose administration)		-28 to -1 (≤28 days)	1	2	4	8	15	22	23	25	29	36	43	44	46	50	57	64	85	106	134	
Cycle Visit Day		-	1	2	4	8	15	1	2	4	8	15	1	2	4	8	15	1	1	1	-	
Visit Window (days)		-	see foo	tnote 2	±12h			±3d		±12h			±3d		±12h			±3d	±3d	±3d	±7d	

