3. OBJECTIVES AND ENDPOINTS

The objectives and corresponding endpoints are presented in Table 3-1.

Table 3-1 Objectives, endpoints and statistical considerations

Objectives	Endpoints	Hypothesis	Primary Analysis Population	Timeframe/Time Point
Primary				
To demonstrate superior efficacy of xevinapant vs placebo when added to chemoradiotherapy (CRT) in locally advanced squamous cell carcinoma of the head and neck (LA-SCCHN)	EFS as assessed by the BIRC defined as the time from randomization to the first occurrence of any of the following events: Death from any cause. Progression: Radiological, assessed per RECIST v1.1 or Clinical, with or without RECIST v1.1-radiologically documented progression, assessed endoscopically. Primary treatment failure before achieving a CR: requirement for radical salvage surgery that includes the primary tumor site, with documented viable tumor presenting anatomopathological findings even in the absence of formal RECIST v1.1 radiological progression. Any radiological or clinical relapse after achieving a CR (locoregionally), including any event defined as locoregional treatment failure, even in the absence of formal radiological progressive disease confirmation: Requirement for radical salvage surgery that includes the primary tumor site, regardless of anatomopathological findings or Elective neck dissection or biopsy, with positive viable tumor cells on anatomopathological findings at 22 weeks or later after randomization. Second cancers unless anatomopathological findings exclude squamous histology. Note: Investigator-assessed EFS will be used for supportive analysis.	Xevinapant prolongs EFS in previously untreated patients with LA-SCCHN, compared to matched placebo when administered in combination with platinum-based chemotherapy and intensity-modulated radiotherapy (IMRT).	Intent-to-treat	- From randomization to the earliest between any EFS event or EOS Rate at 9, 12, 18, 24, 30 and 36-months post-randomization.

Objectives	Endpoints	Hypothesis	Primary Analysis Population	Timeframe/Time Point
Secondary			'	

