8.2. Efficacy Assessments

Assessment of tumor response to treatment will be assessed locally and centrally according to the Response Evaluation Criteria in Solid Tumors (RECIST v1.1) but will also take into consideration clinical, anatomopathological, and functional assessments of the tumor, as described in Appendix 13.5.

Tumor assessment and HRQL questionnaires or assessments should be continued until disease progression (as per RECIST v1.1) occurs or Month 60 post-randomization, whichever occurs first.

Participants who progress (as per RECIST v1.1) will enter the OS follow-up period at the time of the event and will be followed up for survival status at least every 3 months, until the EOS (see Section 7.2).

In case of premature discontinuation of treatment in participants without disease progression according to RECIST v1.1 (e.g., unacceptable toxicity), efficacy assessments will continue to be performed until an EFS event has been determined or Month 60 post-randomization, whichever occurs first.

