If a new lesion is equivocal, either continued therapy and follow-up evaluation or biopsy and histological examination will clarify if it represents truly new disease. If repeat scans or biopsy confirm a new lesion, then PD should be declared using the date of the initial scan.

In case histopathological results of a new lesion unequivocally reveal a non-squamous histology of the new malignant lesion, this will not be counted as disease progression within the primary or secondary endpoints of this study.

Evaluation of disease status at each post-baseline timepoint

For participants with measurable disease, the assessment of response status at each timepoint will be an *amalgamation* of the individual response statuses of target lesions, non-target lesions and new lesions, and is shown in Table 3 below.

Table 3 Timepoint Assessment of Disease Status by Imaging for Participants with Measurable Disease at Baseline.

	Timepoint response in:			
Target Lesions	Non-Target Lesions	New Lesions	Overall Timepoint Response	
CR	CR	No	CR	
CR	Non-CR/non-PD	No	PR	
CR	NE	No	PR	
PR	Any, except PD or NE	No	PR	
SD	Any, except PD or NE	No	SD	
Not all measured	Any, except PD	No	NE	
PD	Any	Yes or no	PD	
Any	PD	Yes or no	PD	
Any	Any	Yes	PD	

CR=complete response, NE=not evaluable, PD=progressive disease, PR=partial response, SD=stable disease.

The RECIST papers referenced in this document provide no similar assessment paradigm for response status at timepoint for participants with evaluable but non-measurable disease at baseline, but one can be derived from the information above, and it is provided in Table 4 below.

Table 4 Timepoint Assessment of Disease Status by Imaging for Participants with Nonmeasurable Disease at Baseline, or due to Biopsy or Excision

Timepoint response		Overell Timeneint Beenenee	
Non-Target Lesions	New lesions	Overall Timepoint Response	
CR	No	CR	
Non-CR/non-PD	No	Non-CR/non-PD	
NE	No	NE	
PD	Yes or no	PD	
Any	Yes	PD	

CR=complete response, NE=not evaluable, PD=progressive disease.

Special points

Impact of biopsy and excision. Due to biopsy or excision of target lesions, some participants with measurable *disease* at baseline may have a timepoint response or best overall response of Non-CR/Non-PD

Symptomatic progression. Symptomatic progression alone is not a determinant of disease progression in this *study.*

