14.1 Primary Efficacy Endpoint: Event-free Survival (EFS)

Event-Free Survival (EFS) time is defined as the time (in months) from randomization to the first occurrence of any of the following events as assessed by the BIRC: death due to any cause, disease progression (radiological or clinical), primary treatment failure, relapse (radiological or clinical) or occurrence of a new cancer (see Table 1). Death as reported on the eCRF page "Death" will also be considered in the derivation of EFS time.

$$EFS = (date of EFS event - randomization date +1) / 30.4375$$

Censoring rules for the primary and sensitivity analyses of EFS are described in Table 4 below. The last adequate tumor assessment is defined as the last tumor assessment result that is not "Not evaluable" or "Not assessed". If a participant is meeting a multiple censoring situation, the earliest censoring criterion will be applied.

Table 4: Censoring rules for EFS

Situation	Primary	Sensitivity #1	Sensitivity #2
No evaluable baseline or post-baseline assessment*	Right censored at the date of randomization	Right censored at the date of randomization	Right censored at the date of randomization
Death, PD or any event entering in the definition of EFS after 2 or more consecutive missing or inadequate tumor assessments	Right censored at last adequate assessment before the consecutive missing/inadequate assessments	Right censored at last adequate assessment before the consecutive missing/inadequate assessments	Not applicable
Initiation of a new anticancer treatment for the disease under investigation before any event entering in the definition of EFS	Right censored at their last adequate assessment before the initiation of the new anticancer treatment	Not applicable	Not applicable
No death, PD, nor any event entering in the definition of EFS	Right censored at the date of their last adequate assessment	Right censored at the date of their last adequate assessment	Right censored at the date of their last adequate assessment

Abbreviations: EFS: Event-free survival; PD: Progressive disease

^{*}Any EFS event is considered as a post-baseline assessment.

Table 5: Estimand Attributes EFS

Objective	Estimand Attributes
Primary	

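### Figure 1-2 moves any participant with a second cancer to survival-only follow-up, although a proven non-squamous second cancer is not an EFS event and Sections 1.3 and 8.2 keep such participants under tumour assessment

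*Protocol*

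**What the plan says.** **When EFS follow-up ends.** The protocol gives two kinds of trigger.

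- Figure 1-2 (Section 1.2) states that, at any time in the study, "in case of progression, treatment failure, local or distant relapse or second cancers, subjects will enter the OS follow-up period". From then on only survival is followed. No histology condition is attached.
- Section 1.3 describes those who reach the end of EFS follow-up as "Participants without any progression, treatment failure, local or distant relapse, second cancers or death until Month 60 post-randomization". Table 1-3 footnote 1 uses the same list, also unqualified.
- Section 1.3 also says "Participants who progress according to RECIST v1.1, will enter the OS follow-up period at time of the event". Table 1-1 footnote 11 and Table 1-3 footnote 1 name the same RECIST trigger.
- Section 8.2 agrees: "Participants who progress (as per RECIST v1.1) will enter the OS follow-up period at the time of the event". It adds: "Tumor assessment and HRQL questionnaires or assessments should be continued until disease progression (as per RECIST v1.1) occurs or Month 60 post-randomization". For participants who stop treatment early without progression, Sections 1.3 and 8.2 continue efficacy assessments until an EFS event or Month 60.

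**What counts as an event.** Protocol Table 3-1 and SAP Tables 1 and 5 list as an EFS component: "Second cancers unless anatomopathological findings exclude squamous histology". For a new lesion proven non-squamous, protocol Appendix 13.5 states that "this will not be counted as disease progression within the primary or secondary endpoints of this study".

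**How gaps are censored.** SAP Table 4 (matching protocol Table 10-5) covers this case: "Death, PD or any event entering in the definition of EFS after 2 or more consecutive missing or inadequate tumor assessments". Such a participant is censored at the last adequate assessment before the gap under the Primary and Sensitivity #1 rules; Sensitivity #2 does not apply the rule. A participant with no event is censored at the last adequate assessment under all three. New anticancer treatment triggers censoring only if it is for the disease under study. SAP Table 5 counts a death falling within two missing scheduled assessments as an event.

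**The concern.** Take a participant with a biopsy-proven non-squamous second cancer, no RECIST progression and no other EFS event. Under the figure, tumour assessment ends. Under Section 8.2 it goes on. A site cannot do both.

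The SAP assumes that such a participant remains under observation. The second cancer is not an event, and treating it does not trigger the new-treatment censoring rule. If scans have stopped, later locoregional or distant failures are not looked for, and some later events fall outside the primary analysis because of the gap. The same applies to PFS, which has the same censoring rows, and to LRC, where the gap rule applies to progression.

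Two consequences matter. Ascertainment of the BIRC-assessed primary endpoint depends on which part of the protocol a site follows, across about 280 sites. And a second cancer plausibly raises mortality, so censoring that starts with its diagnosis may be informative.

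**Working it through.** **Step 1. One case, read under each text.** Assume that the last adequate scan is at Month 9 and a non-squamous second cancer is proven at Month 10, with no progression of the study disease.

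- EFS definition and Appendix 13.5: no event, no progression.
- Figure 1-2: moves to survival-only follow-up, so the Month 12 scan is not done.
- Sections 1.3 and 8.2, RECIST trigger: stays in EFS follow-up, and the Month 12 scan is done.

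**Step 2. The same case in SAP Table 4, if the site follows the figure.** Months 12 and 15 are missed.

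- Death at Month 14: one assessment missed, so it counts as an EFS event.
- Death at Month 20: two or more missed, so it is censored at Month 9 under Primary and Sensitivity #1. It is an event under Sensitivity #2 and in OS.
- Alive at cut-off with no recorded event: censored at Month 9 under all three rules. Any relapse in between goes unseen.

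**Step 3. How long a death still counts.** The schedule is EOT at Day 134 (134 / 30.4375 = 4.4 months), then Months 7, 9 and 12, every 3 months to Month 36, and every 6 months to Month 60. The window runs from the last adequate assessment to the second scheduled assessment after it (visit tolerances ignored).

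- Last scan at EOT: 9 − 4.4 = 4.6 months.
- Last scan at Month 7: 12 − 7 = 5 months.
- Last scan at Months 9 to 30: 6 months.
- Last scan at Month 33: 42 − 33 = 9 months.
- Last scan at Months 36 to 48: 12 months.

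So a death is censored only if it comes later than about 4.6 to 12 months after the last adequate scan.

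**Step 4. The plan's own power figure.** SAP Table 3 gives 88.2% for EFS with looks at 279, 365 and 429 events, HR 0.73 and one-sided alpha 0.025. Recomputing with Lan-DeMets O'Brien-Fleming-type spending gives boundary p-values of 0.0054, 0.0135 and 0.0202 (stated 0.005, 0.013, 0.020). Simulated power, with the futility bound applied at the first look, is 88.3%. The figure reproduces and is not in dispute. Single-look Schoenfeld power, used below for comparison, is Φ(√429 / 2 × |ln 0.73| − 1.96) = Φ(3.259 − 1.960) = 90.3%.

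**Step 5. Illustration of size.** The documents give no rate of second cancers, so both versions below rest on assumptions, and both suppose that every site follows the figure.

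- Version A: events lost = 700 × q × e, where q is the share with a non-squamous second cancer (assumed 1% to 5%) and e is the share of those whose later EFS event is lost (assumed 30% to 60%). Lowest: 700 × 0.01 × 0.3 = 2.1. Highest: 700 × 0.05 × 0.6 = 21. Single-look power on the remaining 426.9 to 408 events is 90.2% to 88.9%.
- Version B: the planning medians of 17 months (protocol 10.2.1) and 23.3 months (SAP Table 2) give hazards ln 2 / 17 = 0.0408 and ln 2 / 23.3 = 0.0297 per month, mean about 0.0353. Then 429 / 0.0353 is about 12,150 person-months, or about 1,010 person-years. At an assumed 0.5% to 2% per year, about 5 to 20 participants are affected. If half would have had an EFS event before cut-off, about 3 to 10 events are lost, without deducting deaths that fall inside the Step 3 window.

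**The case against.** The best reply is that the bare term is shorthand. Section 7.1 uses a similar list and there points to the EFS definition in Table 3-1, which carries the histology exception. The rationale recorded for protocol version 9.0 ties entry into OS follow-up to a first EFS event. Figure 1-2 is a flow summary, and the detailed text and table footnotes use RECIST progression as the trigger. This is good evidence of intent, and it means that stopping scans is not the protocol's settled rule. It does not remove the conflict. The figure has no such pointer, and Section 1.3 and Table 1-3 footnote 1 themselves repeat the unqualified list.

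Three stronger readings are tempting, and the documents do not support them.

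- A reader might infer that every later death is lost from the primary analysis. SAP Tables 4 and 5 count a death before two consecutive missed assessments, Sensitivity #2 does not apply the gap rule, and OS is unaffected.
- A reader might infer from Section 8.2 that scans must continue after an EFS event until RECIST progression. Section 8.2 contains two stop rules: RECIST progression in general, and an EFS event for those who stopped treatment early. The version 9.0 rationale also describes imaging as ending after an EFS event. That is a separate trade-off.
- A reader might infer material bias in the hazard ratio or a serious loss of power. The trial is double-blind, no mechanism that differs by arm is apparent, and the primary analysis is event-driven, so lost events mainly delay it.

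**Conclusion.** The point holds as an internal inconsistency that should be fixed. Figure 1-2, and by implication the Month 60 sentences in Section 1.3 and Table 1-3 footnote 1, treat any second cancer as ending EFS follow-up. The EFS definition and Appendix 13.5 do not count one that is proven non-squamous, and Sections 1.3 and 8.2 keep such a participant under assessment.

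The harm arises only where a site follows the figure. Participants with no later recorded event are then censored early, and events after two or more missed assessments are censored under Primary and Sensitivity #1.

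The size cannot be derived from the documents. Under the assumed rates above it is a few to about 20 of 429 events, with single-look power of at least 88.9% against 90.3%. What remains is inconsistent ascertainment between sites and possibly informative censoring. That the censoring is informative rests on the assumption that a second cancer raises mortality, which is plausible but not quantified in the documents.

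**What to change.** In Figure 1-2, Section 1.3 and Table 1-3 footnote 1, replace the bare term with wording that limits it to second cancers meeting the EFS definition in Table 3-1. Add one sentence: a participant whose second cancer has squamous histology excluded, and who has had no other EFS event, remains in EFS follow-up on the randomization-based schedule.

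Reconcile the two stop rules in Section 8.2 as a separate item; this change does not need to settle whether scanning continues after an EFS event.

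The cost is a wording change in three places and a memo to sites. A small number of participants would have scheduled scans that they would miss under the figure. No change to the SAP censoring rules, event targets or boundaries is needed.

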1.3. Schedule of Assessments

The schedule of the normal completion of the study visits/procedures is presented in Table 1-1. The description of each assessment is detailed in Section 8. It may be necessary to perform these assessments at unscheduled timepoints if deemed clinically necessary by the Investigator.

Screening procedures will start once the participant has signed the informed consent form (ICF). The screening period will start at the ICF signature and can last up to 28 days.

¹⁸F-FDG-PET, intravenous (i.v.) contrast-enhanced CT-scan or MRI of head and neck, and CT-scan of chest are only accepted if they are performed within 4 weeks before randomization. Dental examination, audiometry, HBV/HCV/HIV tests, and fiberoptic endoscopy performed within 2 weeks before ICF signature do not have to be repeated during screening. If several i.v. contrast-enhanced CT scans/MRI of the head and neck and CT scans of the chest are available before treatment start, the closest imaging prior to randomization will be used as baseline (for each participant, the same radiological method must be used throughout the study). Further details on imaging are provided in Table 1-1, Section 8.2.1.

During screening and after randomization, laboratory assessments and pregnancy tests should be performed either by a local laboratory or by a central laboratory designated by the Sponsor according to instructions provided in Table 8-2 in Section 8.3.7.

Results from central laboratory should be used for defining participant eligibility during screening, except for HBV/HCV/HIV tests that may be performed by a local laboratory within 2 weeks before ICF signature (see above and Table 8-2) and human papillomavirus (HPV) status by p16 IHC that may be obtained locally (see Section 8.1.2).

A participant will be considered eligible to receive the study treatments after he/she has signed the ICF, all eligibility criteria have been met and the IMRT plan has been sent to the Radiotherapy Quality Assurance (RT-QA) Review Center (see Section 11.2.2). Randomization can be performed once the participant is considered eligible. The IMRT plan must be approved by the RT-QA Review Center prior to the start of the IMRT.

Study treatment (on C1D1) should begin within 7 days after randomization.

The End of treatment (EOT) visit will be performed 15 days (± 7days) after last study treatment administration (i.e., xevinapant/placebo, chemotherapy or IMRT whichever is administered last), but prior to the start of any subsequent anticancer therapy (see also Section 7.1).

Study procedures must be performed according to the planned visit schedule within the permitted visit windows. During the treatment period, each study visit day and allowed time windows will be based on the C1D1 date. The treatment diagram and time windows for visits during the treatment period are presented in Table 1-2.

NOTE: Renal function monitoring must also take place 48 hours (± 12 hours) after cisplatin infusion (i.e. at C1D4, C2D4, C3D4) based on local laboratory assessments as shown below (see also Table 1-1):

Local Laboratory Sampling	Schedule for Renal Function Monitoring
Creatinine, eGFR Sodium, potassium, calcium, magnesium	C1D4 (within 48±12 hours from C1D2)
Codam, potassiam, calcium, magnesiam	C2D4 (within 48±12 hours from C2D2)
	C3D4 (within 48±12 hours from C3D2)

In case of abnormal renal function parameter(s) or electrolyte disbalance, additional hydration and electrolyte replacement should be considered, as well as cisplatin dose adaptation in the next cycle.

Adequate hydration must be maintained pre- and post-cisplatin infusion according to the following schedule (see Appendix 13.3 for detailed instructions):

Pre-infusion	Post-infusion
2 to 12 hours prior to administration of cisplatin	until minimum 6 hours after the administration of cisplatin

Every attempt should be made to have each participant attend each visit as scheduled. Study visits/procedures performed outside of the allowed visit window will be considered as protocol deviations, with the exception of premature discontinuation from study treatment or withdrawal from the study due to reasons described in Section 7.

The EFS follow-up period must be performed according to the planned visit schedule within the permitted visit windows. Participants without any progression, treatment failure, local or distant relapse, second cancers or death until Month 60 post-randomization, will enter the overall survival (OS) follow-up period after the Month 60 visit (FUP60). They will be followed for survival status only, at least every 3 months, until the End of Study (EOS) (see Section 7.2). Participants who progress according to RECIST v1.1, will enter the OS follow-up period at time of the event and will be followed up for survival status at least every 3 months, until the EOS (see Section 7.2).

In case of premature discontinuation of treatment in participants without disease progression (e.g., unacceptable toxicity), efficacy assessments will continue to be performed until an EFS event has been determined or Month 60 post-randomization, whichever occurs first.

During the EFS follow-up period and OS follow-up period, each study visit day and allowed time windows will be based on the randomization date.

After completion of the follow-up period, participants who have not discontinued the study prematurely will undergo the EOS assessments ([date of the 60 Month visit of the last on-study participant] ± 2 months) and will be considered as having completed the study (see Section 7.2 in case of premature withdrawal).

If the last on-study participant completes the OS follow-up (60 months after randomization), his/her EOS visit will be performed at the same time as his/her 60 Month visit. In case of premature discontinuation from the study, his/her EOS visit will be performed when he/she discontinues from the study.

The EOS visit can be performed by telephone call.

Table 1-1 Schedule of events / flow chart: screening & treatment period

Study Period		Scr		Combination therapy (CRT and Xevinapant/matched placebo) period															Monotherapy (xevinapant or matched placebo) period			
Cycles		-			1					2					3			4	5	6		
Visit Label		Scr	C1D1	C1D2	C1D4	C1D8	C1D15	C2D1	C2D2	C2D4	C2D8	C2D15	C3D1	C3D2	C3D4	C3D8	C3D15	C4D1	C5D1	C6D1	EOT	
Study Week	Section	(≤4 weeks)	1	1	1	2	3	4	4	4	5	6	7	7	7	8	9	10	13	16	20	
Study Visit Day (from 1st dose administration)		-28 to -1 (≤28 days)	1	2	4	8	15	22	23	25	29	36	43	44	46	50	57	64	85	106	134	
Cycle Visit Day		-	1	2	4	8	15	1	2	4	8	15	1	2	4	8	15	1	1	1	-	
Visit Window (days)		-	see foo	tnote 2	±12h			±3d		±12h			±3d		±12h			±3d	±3d	±3d	±7d	
Informed consent	8.1, 11.1.1	Х																				
Tumor staging	8.1.1	Χ																				
Archived tumor biopsy ³	8.5.2	Χ																				
Medical history	8.1.1	Χ																				
Demographics, height	8.1.1	Χ																				
HBV, HCV, HIV tests	8.3.7	X ⁴																				
	5.1, 5.2	Χ																				
Randomization ⁵	6.3	>	(
Height	8.3.2	Χ																				
Physical examination, weight	8.3.1, 8.3.2	Χ	Χ					Χ					Χ					Χ	Χ	Χ	Χ	
ECOG PS	8.3.2	Χ	Χ					Χ					Χ					Χ	Χ	Χ	Χ	
Vital signs	8.3.2	Χ	Χ	Χ				Χ					Χ					Χ	Χ	Χ	Χ	
ECG	8.3.6	Χ	Χ			Χ																
Nutritional status	8.3.3	Χ						Χ					Χ					Χ			Χ	
Dental examination	8.3.4	X ⁴																Χ			Χ	
Audiometry	8.3.5	X ⁴						$(X)^{10}$					$(X)^{10}$					$(X)^{10}$			$(X)^{10}$	
Coagulogram	8.3.7	Χ						Χ					Χ					Χ			Χ	
Blood hematology	8.3.7	Χ	X6, 7			X	Χ	X ⁷			Χ	Χ	X ⁷			Χ	Χ	Χ	Χ	Х	Χ	
Blood biochemistry – full panel	8.3.7	Х	X6, 7					X ⁷					X ⁷					Χ	Χ	Х	Χ	
Blood biochemistry– minimum panel	8.3.7					Х	Χ				Х	Х				Х	Х					
Renal function monitoring ¹⁴					Χ					Χ					Χ							
Pregnancy test ⁸	8.1.3, 8.3.7	Х	X ⁶					Х					Х					Х	Х	Х	Х	
Urinalysis	8.3.7	Х						Χ					Χ					Χ			Χ	

[figure not shown]
Study Period		Scr		Combination therapy (CRT and Xevinapant/matched placebo) period															Monotherapy (xevinapant or matched placebo) period			
Cycles		-		•	1	•			•	2					3	•		4	5	6		
Visit Label		Scr	C1D1	C1D2	C1D4	C1D8	C1D15	C2D1	C2D2	C2D4	C2D8	C2D15	C3D1	C3D2	C3D4	C3D8	C3D15	C4D1	C5D1	C6D1	EOT	
Study Week	Section	-4 to -1 (≤4 weeks)	1	1	1	2	3	4	4	4	5	6	7	7	7	8	9	10	13	16	20	
Study Visit Day (from 1 st dose administration)		-28 to -1 (≤28 days)	1	2	4	8	15	22	23	25	29	36	43	44	46	50	57	64	85	106	134	
Cycle Visit Day		-	1	2	4	8	15	1	2	4	8	15	1	2	4	8	15	1	1	1	-	
Visit Window (days)		-	see foo	otnote 2	±12h			±3d		±12h			±3d		±12h			±3d	±3d	±3d	±7d	
EORTC QLQ-C30 and EORTC QLQ-HN35 questionnaires	8.6	Х																Х			Х	
C																						
¹⁸ F-FDG-PET	8.2.1	X ⁴																			Χ	
i.v contrast-enhanced CT-scan or MRI of head and neck AND CT-scan of chest	8.2.1	X ⁴																			X ¹³	
Clinical tumor assessment of ear, nose and throat examination and fiberoptic endoscopy	8.1.1, CCI	X ⁴																			х	
C																						
Xevinapant / matched placebo administration	6.1.2.1, Table 1 -2		F	rom Da	y 1 to 14	1		F	rom Da	y 1 to 14	1		F	rom Da	y 1 to 14		From Day 1 to 14	From Day 1 to 14	From Day 1 to 14			
Participant diary dispensation	8.3.8		Χ																			
HD-CDDP or CBCDA	6.1.2.2, Table 1 -2			Х					Х					Х								
IMRT	6.1.2.3, Table 1 -2				X X X X X 5 fractions/week for 7 weeks																	
EFS data collection ¹¹	8.2		←																	\rightarrow		
Concomitant medication	6.5		←																	\rightarrow		
Adverse events	8.3.10, 9		←																	\rightarrow		
SAEs and late onset AESIs	9.1.4										-										Х	

Xevinapant TrilynX M202359 0006

Abbreviations: AESI: adverse event of special interest; CBCDA: carboplatin; CRT: chemoradiotherapy; CT-scan: computed tomography scan; d: days; Cx	Dx:
Cycle x Day x; ECG: electrocardiogram; eCRF: electronic case report form; ECOG PS: Eastern Cooperative Oncology Group Performance Status; EFS: event-	ree
survival; EORTC: European Organisation for Research and Treatment of Cancer; EOS: end of study; EOT: end of treatment;	
HBV: hepatitis B virus; HCV: hepatitis C virus; HD-CDDP: high-dose cisplatin; HIV: human immunodeficiency virus;	PV:
human papilloma virus; IMRT: intensity-modulated radiotherapy; i.v.: intravenous; MRI: magnetic resonance imaging; OPC: oropharyngeal cancer; OS: over	rall
survival; burning and the state of the stat	

- 1. The EOT visit will be performed 15 days (± 7days) after last study treatment administration (i.e., xevinapant/placebo, chemotherapy or IMRT whichever is administered last) but prior to the start of any subsequent anticancer therapy.
- 2. C1D1 and C1D2 are triggered by the 1st dose administration of xevinapant/matched placebo and HD-CDDP, respectively. These visits should be performed on consecutive days (see also Table 1-2).
- 3. Participant should be willing to provide an archival tumor sample for exploratory purposes (except for China), if available; it should also be used for HPV status definition by p16 IHC testing (in participants with OPC) if no local report is available. See Sections 8.4.2 and 8.5.2.
- 4. ¹⁸F-FDG-PET, i.v. contrast-enhanced CT-scan or MRI of head and neck, and CT-scan of chest are only accepted if they are performed within 4 weeks before randomization. Dental examination, audiometry, HBV/HCV/HIV tests, and fiberoptic endoscopy performed within 2 weeks before ICF signature do not have to be repeated during screening.
- 5. Treatment on C1D1 should be initiated within 7 days after randomization.
- 6. On C1D1, hematologic, renal and hepatic laboratory assessments (as required in inclusion criteria 10, Section 5) and pregnancy status (assessed by urine or serum test) should not be repeated locally if latest results (assessed by central laboratory) are within 7 days prior to the 1st dose administration (see also Table 8-2).
- 7. On C1D1, C2D1 and C3D1, suitability for chemotherapy administration (see Section 6.1.2.2) should be checked by a local laboratory (see exception on C1D1 in Table 8-2). Suitability for CRT administration must be documented in the participant medical record.
- 8. Serum pregnancy test during screening will be performed by a central laboratory in women of childbearing potential. Negative pregnancy status should be rechecked locally (serum or urine test) on C1D1 before first dose administration if the assessment was performed more than 7 days before. After C1D1, a urine or serum pregnancy test should be performed by a local laboratory (see also Table 8-2).
- An audiometry must be performed at screening. In addition, a hearing clinical evaluation and an audiometry should be performed at C2D1 and C3D1 if clinically indicated (except for France, see Appendix 13.6) and at any time if clinically indicated as per institutional or national guidelines.
- 11. After progression (according to RECIST v1.1), at any time during the study, participants will enter the OS follow-up period and will be followed up for survival at least every 3 months until EOS (see Table 1-2and Section 7.2). Survival follow-up can be performed by telephone calls.
- 13. Response confirmation is not required. In case of doubt of a clinical locoregional recurrence or distant metastasis before the EOT, imaging by CT/MRI scan should be performed to confirm the disease progression.
- **14.** Renal function monitoring 48 hours (±12 hours) after cisplatin infusion (i.e at C1D4, C2D4 and C3D4) based on local laboratory assessments (see Table 8-2) and hydration recommendation (see Appendix 13.3 for instructions).

Table 1-2 Treatment diagram and time window for visits

Abbreviations: C: cycle; CBCDA: carboplatin; CRT: chemoradiotherapy; EOT: end of treatment; HD-CDDP: high-dose cisplatin; IMRT: intensity-modulated radiotherapy; W: week.

^a On days when IMRT and chemotherapy are to be administered,

On days when IMRT is to be administered without chemotherapy, xevinapant or matched placebo should be preferably administered before IMRT.

